Essex Coronavirus Action Support (ECAS) involves collaboration between Essex County Council (ECC) and The Essex Public Health Team as well as local Facebook groups. It focuses on the provision of three services: *preventing* the spread of infection, *informing* Essex residents of guidance and *assisting* residents who may be vulnerable. The ECAS Facebook page which was created on 14th March 2020 ('Essex Coronavirus Action', 2020) is now followed by 55,339 people (at the time of writing) and is used to distribute information to the community. The related private group created on 15th March 2020 has approximately 37,900 members ('Essex Coronavirus Action Support', 2020) and is described as a space for residents of Essex, promoting connection and discussion about issues related to the COVID-19 pandemic.

When membership of the ECAS group is requested, admins ask for a postal code to verify people are Essex residents, members are not actively recruited. Whilst approximately 80% of the demographic is female, men have been reported to be over-represented in discussion ('Mobilizing Essex residents', 2020). There are 18 community admins who oversee the private group, three have a prominent role with ECC paying for their work. Issues around misinformation are dealt with on a case-by-case basis and in rare instances members are banned/ muted if promoting argument.

Growth, recruitment and management have been described as evolving intuitively and some research has been conducted to capture decisions explicitly in terms of team roles, structure and the organisational environment ('Essex County Council', 2021). The co-produced logic model illustrating resources, activities and outcomes as well as their connection (shown in Figure 1) guides the current evaluation of the ECAS intervention.

The proposed evaluation will combine quantitative (Work Package 1, see *Methods* below) and qualitative (Work Package 2) methods to understand the extent to which ECAS achieved its aims to facilitate 'prevent, perform and assist' and also the wider impact it has had on public health system approaches.

Rationale

Promoting behavioural change

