Effects of ECAS and underlying processes: For those that have joined ECAS, we will test how engagement with the ECAS Facebook page and group relates to (i) a sense of social connection and (ii) how both engagement and the sense of social connection relate to the interim outcomes of increased health literacy, covid protective behaviour and community champion activity (see Figure 2). A further analysis will compare levels of each of these factors amongst those who did engage with the intervention versus a comparator group who did not and across socio-demographic groups if the data allows (i.e., using moderation analyses). Amongst both samples, we will also measure current levels of mental health and test relationships between these and each factor. These analyses will provide a quantitative evaluation of the extent to which the intervention met its aim to ‘inform’, ‘prevent’ and ‘assist’. Additionally, for those who engage in it, it will also identify which interim outcomes were most impacted and the extent to which this effect was mediated by social connection.

[figure not shown]

Figure 2: Primary conceptual model to be tested.

Given the nature of the study, much of these data will be retrospective (i.e., people’s recollection of their behaviours). In these instances, we will ask participants to recall how they felt during what our preparatory work with stakeholders (stakeholder workshops and also a PPIE workshop), identified as a *critical phase* of the intervention’s deployment. The critical phase selected for the quantitative analysis of new data is the the first two weeks following the lifting of the first lockdown.

Table 1 (see below) indicates broad operationalisations of each of the factors, the source of data (and whether it is current or retrospective) and possible measurement instruments.

Table 1: Indicative primary outcome measures¹

Factor	Operationalisation(s)	Source of data	Indicative instrument
Interaction with ECAS	Did / did not engage with site Intensity of engagement (users only)	Facebook data or self-report	Study generated scale/metrics
Social connection	Sense of social connection with others Collective responsibility	Self-report (current) Self-report (critical phase)	Validated scale (Lee, Draper & Lee, 2001)
Health literacy	Level of perceived digital health literacy	Self-report (current)	Use of two subscales: information searching and evaluating reliability from validated scale (Van der Vaart & Drossaert, 2017)

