Work Package 1: We will aim to recruit a sample of $n = 225$ people who have signed up to the ECAS Facebook page and group. We will also recruit a comparative, equally sized sample of Facebook users who did not sign up to the page nor recall being exposed to it. These will be either a comparative demographic profile, or we will weight responses to match our samples. Recruitment will be conducted via Facebook. The total target sample size will be $n = 450$. See *Recruitment*, below, for details on how these samples will be secured.

Inclusion criteria:

- 18+ years of age
- Facebook user
- Enrolled in ECAS page and group on Facebook (ECAS condition only)
- Works or lived in Essex during first lockdown period

Exclusion criteria:

- Enrolled in ECAS page and group on Facebook (comparator condition only)
- Unable to give informed consent

Social network analysis: Data will be collected from the ECAS group page drawing on posts made (i) during the first two weeks of the first lockdown and (ii) the first two weeks following the lifting of the first lockdown. In each period, the highest day traffic will be selected, then the lowest (non-contiguous) day and then the non-contiguous day closest to the mean. We will manually sample and code 800 contiguous interactions per day, three days per phase (total $n = 2400$ interactions).

Size of sample

Primary analysis sample: Our within condition sample of $n = 225$ allows detection of single mediation effects at power = 0.81 assuming medium (Pearson $r = .30$) relationships between variables (calculated using 'pwr2ppl' R package 'med' function). In the absence of suitable pilot data, these levels of relationship have been selected as they represent effects which are likely, and are in line with relationships between social identity and efficacy and behaviour observed in other studies (i.e., Frings, Wood & Albery, in press). Relationships smaller than that powered for are also likely to be of less practical significance. A sample sufficient to power multiple mediation models is beyond the scope of the current study.

Social network analysis: This sample size indicated above balances a manageable amount of data inputting and sufficient data to generate meaningful insight. Focusing on high and low traffic days gives a representation of time the group is seeking and receiving information from the centre of the network and times when they are engaged in more general interaction.

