Work Package 2: Sampling techniques for each aspect are detailed in Table 2.

Table 2: Recruitment methods for Work Package 2

Research method	Sample and sampling technique
Discourse analysis of online Facebook conversations	
Facebook posts, comments and discussions will be analysed in samples of 1-2 weeks at key points:
 
• The initial lockdown and set up phase (March-April 2020)• Interim period between the first and second lockdowns (July/August 2020)• The second lockdown (Oct-Nov 2020)• Interim period between the second and third lockdowns (July/August 2020)• The third lockdown (Jan 2021) 
This will enable the analysis of each lockdown as well as comparison with lower activity periods between these active periods

Qualitative semi-structured interviews	
A total population sampling strategy will be used to purposively sample all staff within Essex Public Health and the Facebook admin team:
 
Key Essex County Council staff who designed the intervention (n = 5-6)
 
Facebook admins (n = 6-8)
 
Wider staff within the Essex Public Health team (n = 6-8)
 
Total sample = 17-22 participants

Sampling technique

Work Package 1: The study will draw upon a convenience sample of individuals recruited from the ECAS platform, and the comparative sample from Facebook in line with the inclusion and exclusion criteria above. Our health equity analysis will help us to evaluate the extent to which the chief samplers are representative of the ECAS population and the wider population of Essex. Should the sample be non-representative, we will explore the need to weight responses accordingly.

Social network analysis: Purposive sampling will be undertaken to capture representative patterns of activity - please see *Sampling* (above).

Work Package 2: See Table 2 for sampling techniques.

Recruitment

Work Package 1: Where new data are collected, we will recruit directly for the ECAS group via a series of posts promoting the study. For the comparator sample, a range of community Facebook groups will be contacted (with permissions to post sought from moderators where the group's usage terms require this), supported by paid posts promoting the study to the target population. We will incentivise both groups via use of vouchers.

For the *social network analysis*: please see *Sampling* (above).

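### The ECAS arm is drawn from people still enrolled in 2021 but asked about mid-2020, so members who have since left have no stated way in, and the eligibility wording does not say which arm they belong to

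*Protocol*

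**What the plan says.** The Sampling technique section describes the ECAS arm as a "convenience sample of individuals recruited from the ECAS platform". The Recruitment section gives the route: "we will recruit directly for the ECAS group via a series of posts promoting the study". The comparator is sought through a range of community Facebook groups and paid posts.

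Eligibility for Work Package 1 is worded in four places under Sampling:

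- ECAS arm, running text: "people who have signed up to the ECAS Facebook page and group".
- ECAS arm, inclusion criterion: "Enrolled in ECAS page and group on Facebook (ECAS condition only".
- Comparator, running text: "Facebook users who did not sign up to the page nor recall being exposed to it".
- Comparator, exclusion criterion: "Enrolled in ECAS page and group on Facebook (comparator condition only".

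The recall window for the retrospective measures is "the first two weeks following the lifting of the first lockdown" (Primary analyses of new data). Table 1 assigns protective behaviour and community champion activity to that window. It assigns digital health literacy to the present, and social connection partly to each. The Milestones table completes data collection in November 2021.

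Two safeguards are mentioned. Sampling technique says that, if the sample proves unrepresentative in the health equity analysis, the need for weighting will be explored. The risk register names a market research panel in case recruitment fails, and the Milestones table has a panel-liaison entry with no date.

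**The concern.** Entry to the ECAS arm depends on still being in the intervention more than a year after the period under study. Entry to the comparator arm carries no matching condition. If staying is related to how well ECAS suited a person, the arm holds more of those it suited than the 2020 membership did.

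Two analyses are exposed. The ECAS-versus-comparator analysis feeds the judgement on whether ECAS met its aims, and Work Package 3 uses the same comparator for costs per unit of change. The within-ECAS mediation test, for which the sample was sized, uses intensity of engagement as predictor, and people who left or stopped reading probably sit at its low end.

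The weighting does not reach this. It is optional and tied to a demographic comparison, so it cannot correct selection on engagement or satisfaction among people of the same demographic profile. A larger sample would not remove it either.

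**Working it through.** **1. Where a former member falls.** Take someone who joined in spring 2020, was active in the recall window and left in early 2021.

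| Rule | Result |
|---|---|
| ECAS running text (has signed up) | Can be read as qualifying |
| ECAS inclusion criterion (enrolled) | Does not qualify if read as current status |
| Comparator running text (did not sign up) | Does not qualify |
| Comparator exclusion (enrolled) | Not excluded if read as current status |

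On the running text this person is an ECAS participant. On the listed criteria the person is barred from the ECAS arm and not barred from the comparator. The four lines cannot all be applied together. A lapsed reader who never left is eligible on any reading and is simply harder to reach by posts.

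**2. The protocol's own power figure.** Inputs from Size of sample: n = 225, all correlations .30, stated power 0.81. Two-sided alpha of 0.05 is assumed, since none is given there. Using the first-order Sobel test:

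- a = .30; b = (.30 − .09)/(1 − .09) = .2308; R² = 2 × .2308 × .30 = .1385.
- SE(a) = √(.91/223) = .0639; SE(b) = √(.8615/(222 × .91)) = .0653.
- z = ab/√(a²SE(b)² + b²SE(a)²) = .0692/.0245 = 2.82; power = Φ(2.82 − 1.96) = 0.81.

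The stated figure reproduces, so the sample-size arithmetic is not at fault.

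**3. Shift in the ECAS mean.** The protocol gives no attrition rate, so both inputs are assumptions: a fraction p of critical-phase members is lost, and they would have scored d = 0.3 SD below those retained. The shift is p × d: 0.20 × 0.3 = 0.06 SD, and 0.33 × 0.3 = 0.10 SD. The difference detectable with 80% power at 225 per arm is (1.96 + 0.84) × √(2/225) = 0.26 SD.

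A second model, with no true effect and a retention propensity correlated .1 to .3 with the outcome, gives spurious differences of:

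- 0.02–0.06 SD with 90% of members reachable;
- 0.05–0.15 SD with 70%;
- 0.08–0.24 SD with 50%.

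**4. Narrowed engagement range, worst case.** Suppose engagement is normal and every lost member is less engaged than every retained one. With k = Φ⁻¹(p) and λ = φ(k)/(1 − p), the retained variance is u² = 1 + kλ − λ², and the observed correlation is .30u/√(.91 + .09u²).

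| Lost | u | Observed r | SE(a) = .0639/u | Sobel z | Power |
|---|---|---|---|---|---|
| 0% | 1 | .30 | .064 | 2.82 | 0.81 |
| 20% | .76 | .23 | .084 | 2.52 | 0.71 |
| 33% | .69 | .21 | .093 | 2.38 | 0.66 |

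The slopes a and b and SE(b) do not change under truncation on engagement; only SE(a) grows. A simulation of the same truncation gave Sobel power of 0.88 with no loss, 0.84 with 90% retained and 0.72 with 70% retained. Its starting point is above the formula's, so it is best read as relative loss, and it points the same way.

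**The case against.** The strongest objection is that the size rests on assumption. Nothing in the protocol says how many members left or why; someone whose need for information was met may leave as readily as someone dissatisfied. The protocol says only that "in rare instances members are banned/ muted if promoting argument", so removals add little. A mean shift of 0.06–0.10 SD is well below the detectable 0.26 SD, and the ECAS-versus-comparator contrast is introduced as a further analysis, not the one the sample was sized for. The comparator is also recruited partly from people reading community groups in 2021, so it is not free of selection on current Facebook use. All of this stands. It limits the claim about size and direction but does not supply a route in for leavers.

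A reader might infer that a post inside the private group is the only way into the ECAS arm. The text does not go that far: the platform includes the page as well as the group, and a panel is held in reserve. These routes could reach lapsed readers, who remain enrolled. They would not help leavers if the enrolment criterion is read as current status.

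A reader might also infer that the contrast is biased in favour of ECAS as a matter of fact, or that a correlation of .30 could shrink to about .16. The first is an expectation that the documents do not measure. The second needs u = 0.5, which under the truncation model means losing about 73% of members, far beyond a 20–33% loss.

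Finally, the protocol openly calls this a convenience sample and plans a representativeness check. That is candid, but the check is demographic.

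**Conclusion.** The point holds in a limited form. The inconsistency in the eligibility wording is on the page and needs reconciling whatever the size of any bias. The selection on continued membership is also built into the plan, and the stated weighting does not address it. Its effect is plausible, not shown. Under an assumed 20–33% loss, the ECAS mean would be inflated by about 0.06–0.10 SD if those lost score 0.3 SD lower. In the worst case for engagement, r = .30 would be seen as about .21–.23 and mediation power would fall from 0.81 to about 0.71–0.66. Less systematic loss would do less harm. This is a worthwhile, low-cost improvement, not a flaw that invalidates the design.

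**What to change.** 1. Reword the ECAS inclusion criterion to: was a member of the ECAS page/group during the critical phase, whether or not still enrolled. Bring the running text under Sampling into line.
2. Change the comparator exclusion to ever enrolled, so that it matches the comparator definition.
3. Add one screening item on membership (current, former, never) to the common survey. Former members reached through the community-group and paid posts planned for the comparator are then routed to the ECAS arm.
4. Report the ECAS results with and without former members.

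The cost is two reworded criteria, one survey item and one additional presentation of results, with no extra participants. The protocol shows no budget for paid posts, so any widening of them should be costed. With 225 places, former members would take the place of some current ones. Past membership would be self-reported, and former members may be too few for the with-and-without comparison to be informative. Even then, their number would be recorded and they could not enter the comparator arm under the criteria.

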Work Package 2: Qualitative component 2 (semi-structured interviews): Participants for the qualitative semi-structured interviews are all employed by Essex County Council and will be contacted via their work email addresses.

Ethical and regulatory considerations

Informed consent

Work Package 1: New data analysis sample: A participant information sheet will be provided to all participants giving them full information on the studies' aims, methods and risks, etc. Contact details will be provided for participants to ask questions prior to taking part. Once participants have read this, they will give written consent to participate in the study and for use of the data. This PIS and consent form will undergo automated readability checks and be reviewed by our PPIE panel and also approved by LSBU University Ethics Panel (UEP).

Work Package 1: Social network analysis: No consent will be sought from group members, however all data will be anonymised at the point of encoding into the dataset. Sensitivities around data use have and will also be discussed with the PPIE group. Permission to use data in this way will also be sought from the group's administrator and also LSBU UEP.

Work Package 2: Qualitative semi-structured interviews: A participant information sheet will be provided to all participants giving them full information on the studies' aims, methods and risks, etc. Contact details will be provided for participants to ask questions prior to taking part. Once participants have read this, they will give written consent to participate in the study and for use of the data. This PIS and consent form will undergo automated readability checks and be reviewed by our PPIE panel and also approved by LSBU UEP.

Ethical oversight

The research will receive ethical oversight from LSBU UEP and also Essex County Council as required. This oversight will include the study protocol and all participant facing documentation, and a favourable opinion will be secured before any data collection takes place. Any adverse events will be reported to the above bodies.

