Qualitative component 2: semi-structured interviews: The key ethical risk here is that participants will be asked to recall experiences which occurred over lockdown, which may be upsetting for people. We will mitigate this by fully informing participants of the content of the study in advance and providing support and debriefing if necessary during the interview.

Assessment and management of risk

Table 3: Risk register

Key risk	Likelihood	Impact on participants	Impact on project	Mitigation
COVID19 interferes with staff availability (research team + stakeholders)	Moderate	N/A	Moderate	Depth of team, clear project planning to facilitate handover, lines of alternative communication established, agreement to support the evaluation through a Memorandum of Collaborations between LSBU and ECC
Failure to recruit to quantitative strand	Moderate	N/A	High	Guidance from PPIE in planning stage Leverage market research panel resources
Data not available from partners	Low	N/A	Moderate	Agreement with partners on data, ongoing stakeholder involvement Agreement in place to support the evaluation through a Memorandum of Collaborations between LSBU and ECC

Amendments

Significant amendments to the protocol will be discussed in advance with the PHIRST London Central Executive Committee and PH Essex. Should these discussions suggest a need for consultation with the NIHR, this will be co-ordinated by PHIRST London.

Peer review

This protocol will receive a proportionate review by PHIRST London and the NIHR.

Patient & Public Involvement and Engagement

The workshops that informed this design were attended by three Essex community members who have been involved in the development and implementation of ECAS. As these members also received a financial recompense from ECC for their involvement, we extended our PPIE strategy to establish a PPIE Advisory Panel made up of ECAS users and Community Admins involved on a voluntary basis. The project aims to have in place a PPIE Advisory Panel of five members in total. Recruitment was undertaken through advertising on the Facebook page and targeted recruitment for Admin. Three panel members have been active so far and further recruitment is ongoing.

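### The only interview recruitment route, council work email to council employees, does not fit the protocol's own account of the Facebook admins and, on the likely reading, misses the target of 6-8 admins

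*Protocol*

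**What the plan says.** Under Recruitment, Work Package 2, the protocol states that participants in the semi-structured interviews "are all employed by Essex County Council and will be contacted via their work email addresses". No other way of approaching interviewees is described.

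The description of Work Package 2 names three interview groups: council staff behind the design of the intervention, the Essex Public Health Team, and the Facebook admins. Table 2 plans 5-6, 6-8 and 6-8 interviews respectively (admins 6-8), for a total of 17-22. On method it says: "A total population sampling strategy will be used to purposively sample all staff within Essex Public Health and the Facebook admin team".

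Two other places describe who the admins are. The section on the intervention of interest says: "There are 18 community admins who oversee the private group, three have a prominent role with ECC paying for their work". The section on Patient & Public Involvement and Engagement mentions an advisory panel that includes "Community Admins involved on a voluntary basis", and notes that targeted recruitment was used to bring admins onto that panel.

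**The concern.** The Recruitment sentence treats every interviewee as a council employee with a council address. The rest of the protocol describes the admins as community members, a minority of them paid by the council. An admin group of 6-8 must include people beyond the three who are paid, and nothing in the protocol says that those people are employed by the council or have a council address.

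Followed literally, the written route would fall short in the admin group and confine it to paid admins at most. The other two groups are council and public health staff, so the unpaid admins are the interviewees who stand outside the paid delivery organisations. Their absence would also affect Work Package 3. That package wants to capture effects on individuals' own time, and it places its questions on indirect, intangible and opportunity costs in the interview strand. Unpaid admin time is one such cost.

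**Working it through.** **Inputs (all from the protocol)**

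- Council design staff: 5-6 (Table 2)
- Facebook admins: 6-8 (Table 2)
- Wider public health team: 6-8 (Table 2)
- Admins in total: 18, of whom the council pays 3 (The intervention of interest)
- Stated route: council work email only (Recruitment, Work Package 2)

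**Step 1. Reproduce the planned total.** Sum the lower and upper ends of the three groups:

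- 5 + 6 + 6 = 17
- 6 + 8 + 8 = 22

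This matches the stated 17-22 exactly.

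**Step 2. Limit admins to those the stated route may reach.** Let k be the number of admins with a council address. The protocol does not give k. If only paid admins can have such an address, k is at most 3. Being paid is not the same as being employed, so k could be as low as 0. The other two groups are taken as fully reachable by work email, as the Recruitment section says.

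| k | Shortfall against 6-8 admins | Lowest total | Highest total |
|---|---|---|---|
| 3 | 6 − 3 = 3 to 8 − 3 = 5 | 5 + 3 + 6 = 14 | 6 + 3 + 8 = 17 |
| 0 | 6 to 8 | 5 + 0 + 6 = 11 | 6 + 0 + 8 = 14 |

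**Step 3. Compare with the plan.** With k = 3 the range 14-17 touches the planned 17-22 at one value, 17, which requires both other groups to reach their maxima (6 and 8). Totals of 18-22 are out of reach. With k = 0 the highest total is 14, below 17 throughout. The admin target is missed in both cases.

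**Step 4. Check whether admins are in short supply.** They are not: 6/18 = 33% and 8/18 = 44%. The shortfall comes from the stated contact route alone.

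**The case against.** The Recruitment sentence can be read as a loose description of logistics rather than a selection rule. Table 2 sets the sample, and it names the whole admin team. The research team plainly has other access to admins: the stakeholder group includes them, and targeted recruitment has already reached them for the advisory panel. Unpaid admins may well be interviewed in practice. Milestones also gives June 2021 for interview recruitment, before this version of 22 July 2021, so the correction may partly be a matter of recording what was done. All of this is fair. It bears on how likely the shortfall is in practice, but it does not make the sentence consistent with the rest of the protocol, and none of these other routes is stated for the interviews.

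Four stronger readings are tempting, and the protocol does not support them:

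- A reader might infer that the total of 17-22 cannot be reached at all. With three admins, 17 is still attainable.
- A reader might infer that the other 18 − 3 = 15 admins have no chance of selection. The protocol never says that they lack council employment or addresses. The word voluntary in the engagement section may describe service on the panel rather than the admin role.
- A reader might infer that paid admins would give favourable accounts. Nothing in the protocol documents this, and two of the three groups are council or public health staff by design. The interviews are also not the only evidence, since the discourse analysis has its own questions on community building and system change.
- A reader might infer that 6-8 of 18 contradicts total population sampling. It may be the expected yield after inviting everyone. The protocol does not say which is meant.

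**Conclusion.** The contradiction stands: the statement that all interviewees are council employees reached by work email cannot be squared with 18 community admins, three of them paid by the council, and a plan to interview 6-8. On the assumption that only paid admins can have council addresses (0 to 3 reachable), the stated route falls at least 3 to 5 short of the admin target and leaves out unpaid admins. The total is then 14-17, or 11-14 if no admin is reachable, against 17-22. The cap of three is a reasonable inference and not a stated fact, so these figures show what the written route implies and do not forecast the number of interviews. The point is an internal inconsistency that affects who is interviewed. It is no objection to the planned sample size.

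**What to change.** 1. In Recruitment, Work Package 2, replace the employment statement with two routes. Council and public health staff are contacted by work email. Admins, paid or unpaid, are invited through the group's admin channel or by targeted recruitment of the kind already used for the advisory panel.
2. In Table 2, state which is meant: all 18 admins are invited and 6-8 is the expected yield, or 6-8 are purposively selected across paid and unpaid admins.
3. If recruitment has already taken place, record the route that was used.

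The planned interview numbers stay as they are. The cost is protocol and ethics wording and one extra contact channel.
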